3.4. Studies of GVHD Biomarkers

If consent for research samples is obtained, blood samples will be collected on Day -7, day 7, day 14, day 21, day 28, day 56, day 100, day 180, and day 360 post-HCT, as well as at appearance of clinical symptoms suggestive of acute GVHD and that triggers systemic steroid treatment. These samples will be analyzed for the seven-protein biomarker panel. Remaining plasma sample aliquots will be stored for future biomarker studies. Additional, whole blood collected from the recipient on day 56 post-HCT (representing the donor DNA) and day -7 whole blood or saliva DNA (if white blood cells count < $400/\mu$ L) (representing recipient DNA) will be collected, frozen and stored for future genomic studies. Donor chimerism results recorded at the time nearest to each sample collection will be noted. Please note all sample collection days are targets with collection of samples on the closest business day to the suggested day being acceptable.

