2. STUDY DESIGN

2.1. Rationale for study design and objectives

For this study, blood samples will be collected on a calendar basis: Day -7, day 7, day 14, day 21, day 28, day 56, day 100, day 180 and day 360 post-HCT, as well as at appearance of clinical symptoms suggestive of acute GVHD and that trigger treatment with systemic steroids. A saliva sample will also be collected at the day-7 and day +56 time-points from subjects with a HCT white blood cell count of <400/µL to provide an additional specimen for DNA extraction. Samples will be processed at local sites and will then be shipped to the Indiana University Simon Cancer Center (the Data and Specimen Coordinating Center) from the other five participating Blood and Marrow Transplant Programs (Dana-Farber Cancer Institute and Boston Children's Hospital, Johns Hopkins Sidney Kimmel Comprehensive Cancer Center, Fred Hutchinson Cancer Research Center, Texas Children's Hospital, and Children's National Medical Center). The appropriate samples will be transported to [name] laboratory for analysis of a seven-protein biomarker panel. The results from previous discovery and validation studies suggested that the panel of six biomarkers can confirm the diagnosis of acute GVHD in patients at onset of clinical symptoms of acute GVHD and provide prognostic information independent of acute GVHD severity. Furthermore, suppression of tumorigenicity 2 measured at initiation of therapy can predict day 28-non-response and the day 180-post treatment non-relapse mortality in patients with GVHD treated with at least systemic corticosteroids. ST2 outperforms all previously identified biomarkers for prognostic information. The plasma protein biomarker panel will include at minimum: interleukin-2-receptor-alpha, tumor-necrosis-factor-receptor-1, interleukin-8, hepatocyte growth factor, elafin, regenerating islet-derived 3-alpha and suppression of tumorigenicity 2.

Primary Objective: The primary objective is to confirm that ST2 alone or the sevenbiomarker panel measured at initiation of GVHD therapy predict a) D180 post-therapy non-relapse mortality; b) D28 post-therapy non-response, and c) GVHD grade 1-4 onset.

Secondary Objective:

- 1. To demonstrate that ST2 alone or the seven-biomarker panel measured at day 14 or day 21 post-HCT (or a combination of these time points) predict D180 post-HCT non-relapse mortality.

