3. STUDY ENDPOINTS

3.1. Primary endpoint: The primary objective is to confirm that ST2 alone or the seven-biomarker panel measured at initiation of GVHD therapy predict a) D180 post-therapy non-relapse mortality; b) D28 post-therapy non-response, and c) GVHD grade 1-4 onset.

3.2. Secondary endpoints:

- 1. To demonstrate that ST2 alone or the seven-biomarker panel measured at day 14 or day 21 post-HCT (or a combination of these time points) predict D180 post-HCT non-relapse mortality.
- 2. To demonstrate that ST2 alone or the seven-biomarker panel measured at initiation of GVHD symptoms/therapy diagnose acute GVHD as compared to other complications presenting with similar symptoms (drug rash, CMV, Clostridium enteritis).
- 3. To demonstrate that ST2 alone or the seven-biomarker panel measured at initiation of GVHD symptoms/therapy diagnose the severity of acute GVHD at onset and maximum.

3.3. Clinical and histological correlatives:

• Pre-transplant characteristics

Age at transplant, gender, race and ethnicity, Disease diagnosis, disease risk (CIBMTR classification), intensity of conditioning, conditioning regimen, donor source,

HLA-match, stem cell source, other significant pre-HCT diagnoses and clinical characteristics

- GVHD prophylaxis
- Infectious prophylaxis, if any
- Onset Acute GVHD: day of onset, skin stage, liver stage, gastrointestinal stage and overall grade.
- Maximum Acute GVHD: day max, skin stage, liver stage, gastrointestinal stage and max overall grade.
- Biopsies:
 - - yes No,
 - o location skin, upper GI, lower GI, liver
 - GVHD yes or no, other diagnostic, specify
 - This will help identify the incidence of other complications presenting with GVHD symptom that is not GVHD (e.g. infectious diarrhea, drug rash...)
- Systemic therapy
 - Start day
 - Steroids 2 mg/kg/day Yes No
 - Other first line
- Proportion of complete response (CR), Partial response (PR), mixed response, No response, and progression at day 28 post-therapy (among surviving patients)
- Incidence of additional therapy of GVHD given at day 28, and day 56 posttherapy (including for GVHD flare).
- Non-relapse mortality (NRM) at day 180 post-therapy for GVHD patients and NRM at day 180 post-HCT for patients without GVHD.
- Overall survival, GVHD-free survival at day 180 and 360 post-therapy for GVHD patients and NRM at day 180 and 360 post-HCT for patients without GVHD.
- Relapse at day 360 post-HCT.
- Incidence of systemic infections related to GVHD treatment.

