4.2. Study monitoring

The follow-up schedule is outlined in Table 3 (see below).

Table 3: Required assessments													
	All allogeneic HCT, day pre/post-HCT							post-	НСТ	GVHD +	Day post- GVHD systemic therapy		Chimerism
	-7	7	14	21	28	56	100	180	360	Onset (0)	28	56	If Standard of Care in Center
Biopsy of involved tissue (as part of routine clinical care, not research)										х			
Acute GVHD evaluation ^		Х	Х	Х	Х	Х	Х	Х		Х	Х	Х	
Chronic GVHD evaluation ^							Х	Х	Х				
Steroid dose		Х	Х	Х	Х	Х	Х	Х		Х	Х	Х	
Other GVHD medications, doses, and drug levels collected as part of clinical care		x	x	х	x	х	х	x	x	х	х	x	
Blood Samples*	Х	Х	Х	Х	Х	Х	Х	Х	Х	Х	Х		
Saliva DNA (if WBC < 400/µL)	х					Х							
Chimerism (% donor) ‡ **													Х

*Up to day 28, sample collection may be ± 4 days from the target day to allow for scheduling flexibility, holidays, etc...

*Day 100,180, and 360, sample collection will be collected at the clinic visit closest to the scheduled time point to allow for scheduling flexibility, holidays, etc...

*GVHD onset sample will be collected within a 48 hour window of systemic treatment initiation if subject is inpatient

‡ Donor chimerism results recorded at the time nearest to each sample collection will be noted.

^ Refer to Appendix D for GVHD assessment forms

** Will only collect data if already being done as standard of care at center

The timing of follow-up visits is based on the date of BMT and then on the

date of onset of GVHD for post-GVHD assessments.

Assessments

- Baseline weight
- For all, complete acute GVHD staging and grading information including assessment of rash, diarrhea, nausea/vomiting, liver function and weight at day
 - 7, 14, 21, 28, 56, 100, and 180 post-HCT
- If GVHD or GVHD-like symptoms,
 - recommended biopsy of involved tissue (this is standard of care, not research)
 - Complete acute GVHD staging and grading information including assessment of rash, diarrhea, nausea/vomiting, liver function and weight at onset of symptoms and 28 and 56 days post-systemic GVHD therapy
 - Steroids dose weekly until day 56
 - $_{\odot}$ Samples for laboratory studies at day -7, 7, 14, 21, 28, 56,100 and 180

post-HCT and at onset of GVHD symptoms, and 28 days post-systemic

- GVHD therapy
- Chronic GVHD evaluation at day 100, 180 and 360
- Infections requiring therapy up to 360 days post-HCT

Sample Collection

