Samples will be collected at a time when clinical samples are being collected as well if possible. That is, this protocol will NOT require an additional procedure or for a patient's central venous line to be accessed at a time when these things are not being done as part of routine clinical care.

Blood will be collected as part of this study for use in evaluation of biomarkers of HSCT-related toxicities and outcomes and future unspecified research.

 Blood will be collected using the schedule detailed above: day -7 and the following post-transplant days: 7, 14, 21, 28, 56, 100, 180, and 360. Please note that the above blood draw schedule is a target only. Subjects will never be required to come for a clinic visit specifically to have samples collected for the purposes of this study. As such sample

samples collected for the purposes of this study. As such, sample time- points are targets and samples will be collected at the time closest to the target time when collection is feasible. In addition, during inpatient periods, sample collection will take place on the business day closest to

the day scheduled per protocol (to allow for flexibility around weekends and holidays).

- Blood will also be collected at onset of acute GVHD and at day 28 after initiation of steroid therapy.
- In addition, blood will be collected at the onset of other changes in status, which may be clinically significant (such as suspected sinusoidal obstruction syndrome, respiratory distress, relapse, etc.).
- Blood volume to be collected:

Please note cumulative collection volumes at various points in time of participation are summarized in the table below and are detailed for patients >40 kg in text immediately below for clarity.

- Patients > 40 kg: up to 15 mL per time point)
 - 9 scheduled collections in year one = 135 mL
 - 2 scheduled collections in patients who develop acute GVHD = 30 mL
 - Maximum additional blood draws at the time of developing other complications will be set at **four**.
 - 9 scheduled collections + 2 additional collections GVHD collections (if applicable) + maximum of four additional collections with other complications = 15 collections maximum = maximum blood draw of 225 mL.

	Patient Size on Enrollment			
	> 40 kg	25-40 kg	10-25 kg	<10 kg
Maximum volume of each scheduled blood draw	15 mL	10 mL	7.5 mL	5 mL
Maximum volume of blood of each blood draw if develops acute GVHD	15 mL	10 mL	7.5 mL	5 mL

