Children with chronic GVHD can present with skin, GI, eye or systemic disease leading to failure to thrive, persistent immunodeficiency, or pulmonary disease. Chronic "eczema' or dry skin are common manifestations of mild chronic GVHD of skin. Liver disease can present as asymptomatic hyperbilirubinemia or elevated alkaline phosphatase. As children can have marked elevations in alkaline phosphatase during growth spurts, children with this laboratory abnormality should have a fractionated alkaline phosphatase to confirm that the band is from the liver and not from bone before a diagnosis of chronic GVHD is made. Children with chronic GVHD of the upper GI tract may have chronic anorexia or poor growth due to malabsorption. Rather than losing weight, children may "fall off" their growth curve with decreased gains in height or weight velocity. In children < 2 years of age, this may also affect growth of head circumference. Chronic GVHD may also cause persistent low or intermediate immunodeficiency. In addition to increasing the risk of opportunistic infection, this may cause GI dysfunction and lead to malabsorption, low IgG (due to protein losing enteropathy), lactose deficiency, and poor growth. Duodenal intubation with quantitation of pancreatic enzymes is useful in these children. If pancreatic enzymes are low, children may benefit from supplementation of pancreatic enzymes.

See Appendix D for a sample of chronic GVHD data record for use in this trial.

Summary of Required Assessments

- For all subjects
 - complete acute GVHD staging and grading information including assessment of rash, diarrhea, nausea/vomiting, liver function and weight at day 7, 14, 21, 28, 56, 100, and 180 post-HCT
 - Chronic GVHD evaluation at day 100, 180 and 360 post-HCT (please refer to Appendix D for GVHD assessment forms)
 - Infections requiring therapy up to 360 days post-HCT
 - Baseline weight
 - Blood samples for laboratory studies and future use at day -7, 7, 14, 21, 28, 56,100,180, and 360 post-HCT
- For subjects who develop GVHD or GVHD-like symptoms,
 - recommended biopsy of involved tissue (this is standard of care, not research)
 - Complete acute GVHD staging and grading information including assessment of rash, diarrhea, nausea/vomiting, liver function and weight at onset of symptoms and 28 and 56 days post-systemic GVHD therapy
 - Steroid dosing information weekly until day 56 after initiation of steroids

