14. APPENDIX F: LABORATORY PROCEDURES

Research specimens

Research samples collected in this protocol will be used for both protocol-defined testing as well as future, undefined research supporting the protocol. All research sample aliquots will be given unique bar code designations that cannot be linked back to the recipient.

Patient samples will be collected as specified below.

- Peripheral Blood sample on day -7, pre-transplant: Whole blood, Plasma
- Peripheral Blood samples on day 56 post-transplant: Whole blood (donor DNA)
- Donor chimerism results will be recorded at the time nearest to the DNA sample collection
- Peripheral Blood samples at day -7, 7, 14, 21, 28, 56, 100, 180 post-transplant, and if the patient develops GVHD, two additional blood samples at the onset of symptoms that need treatment initiation and 28 days after treatment begins: Plasma

Samples processed into frozen cryovial aliquots will be shipped to the central Laboratory at IU every 6 months on dry ice by Fedex or UPS overnight priority.

Table 6: Collection, processing, and shipping procedures for patient blood samples for protocol-defined biomarker testing and for future undefined research

Time	Collection	Type of processing and	Specimen	Purpose	Shipping specifications
Day -7 pre- transplant	12 mL peripheral blood (two 6 ml fill EDTA purple-top tube)	Centrifuge the EDTA containing whole blood tube at 1000-1300 g or 2100 rpm for 10 minutes within 60 minutes of collection. Remove the separated plasma. Aliquot to 1-4 cryovials and freeze at - 80° C in a scientific grade freezer.	Plasma	Future Biomarker studies	Batch ship every 6 months, frozen on dry ice in a shipping container, Fedex overnight priority to the Well's CCRC Laboratory at IU.
	3 mL peripheral blood (one 3 ml fill EDTA lavender-top tube) Source of patient DNA	Gently mix the tube by gently inverting the tube for 60 seconds and freeze at - 80° C in a scientific grade freezer.	Whole Blood. Until extracted for DNA	Future Biomarker studies	Batch ship every 6 months, frozen on dry ice in a shipping container, Fedex overnight priority to the Well's CCRC Laboratory at IU.

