Day 7 post- transplant	12 mL peripheral blood (two 6 ml fill EDTA purple-top tube)	Centrifuge the EDTA containing whole blood tube at 1000-1300 g or 2100 rpm for 10 minutes within 60 minutes of collection. Remove the separated plasma. Aliquot to 1-4 cryovials and freeze at - 80° C in a scientific grade freezer.	Plasma	Seven protein biomarker panel/ Future Biomarker studies	Batch ship every 6 months, frozen on dry ice in a shipping container, Fedex overnight priority to the Well's CCRC Laboratory at IU.
Day 14 post- transplant	12 mL peripheral blood (two 6 ml fill EDTA	Ficoll (without diluting the blood). Centifuge at 2000 rpm at room temperature for 30 minutes, without brake. Remove the separated plasma. Aliquot	Plasma/ PBMCs	Seven protein biomarker panel/ Future	Batch ship every 6 months, frozen on dry ice in a shipping container, Fedex overnight priority to

	purple-top tube)	to 1-4 cryovials and freeze at - 80° C in a scientific grade freezer. Then collect the "buffy coat" (PBMCs), Wash three times with cold sterile PBS 1X to remove Ficoll (1400 rpm 4C. 10 min.). Count cells. Freeze cells in 1 ml aliquots using 90% FBS and 10% DMSO: 1-5M/vial, at least 2 cryotubes up to 4 cryotubes. Gradual freezing: PBMCs are stored 24 hours (not more) in - 80°C in the ethanol blue box (Cryo-safe cooler , to achieve a -1°C /min. rate of cooling) and then transfer in liquid nitrogen (liquid phase being better than gas phase). See details of the protocol below		Biomarker studies	the Well's CCRC Laboratory at IU.
Day 21 post- transplant	12 mL peripheral blood (two 6 ml fill EDTA purple-top tube)	Ficoll; see protocol below.	Plasma/ PBMCs	Seven protein biomarker panel/ Future Biomarker studies	Batch ship every 6 months, frozen on dry ice in a shipping container, Fedex overnight priority to the Well's CCRC Laboratory at IU.
Day 28 post- transplant	12 mL peripheral blood (two 6 ml fill EDTA purple-top tube)	Ficoll; see protocol below.	Plasma/ PBMCs	Seven protein biomarker panel/ Future Biomarker studies	Batch ship every 6 months, frozen on dry ice in a shipping container, Fedex overnight priority to the Well's CCRC Laboratory at IU.
Onset GVHD treated with systemic steroids	12 mL peripheral blood (two 6 ml fill EDTA purple-top tube)	Ficoll; see protocol below.	Plasma/ PBMCs	Seven protein biomarker panel/ Future Biomarker studies	Batch ship every 6 months, frozen on dry ice in a shipping container, Fedex overnight priority to the Well's CCRC Laboratory at IU.

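### The onset-sample trigger is inconsistent across the protocol, and the panel is assigned at symptom onset only to steroid-treated episodes, so objective 2's look-alikes are selected by the decision the test should inform

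*Protocol*

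**What the plan says.** Secondary objective 2 (protocol synopsis, 2.1 and 3.2) is diagnostic. The markers, measured when GVHD symptoms or therapy begin, are to "diagnose acute GVHD as compared to other complications presenting with similar symptoms (drug rash, CMV, Clostridium enteritis").

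Five places tie the event-driven sample to treatment:
- Section 2.1: "at appearance of clinical symptoms suggestive of acute GVHD and that trigger treatment with systemic steroids".
- Section 3.4: "appearance of clinical symptoms suggestive of acute GVHD and that triggers systemic steroid treatment". It then says that the samples just listed go to the seven-protein panel.
- Table 3 footnote: "GVHD onset sample will be collected within a 48 hour window of systemic treatment initiation if subject is inpatient".
- Appendix F, opening list: "if the patient develops GVHD, two additional blood samples at the onset of symptoms that need treatment initiation".
- Appendix F, Table 6: the only event-driven row whose purpose includes the panel is "Onset GVHD treated with systemic steroids".

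Other places are wider. The Summary of Required Assessments in section 4.2 has a block headed "For subjects who develop GVHD or GVHD-like symptoms", which lists blood at onset with no steroid condition on that draw. The Assessments list under Table 3 is similar. The Sample Collection text in 4.2 asks for blood at acute GVHD onset without mentioning steroids for that draw. It adds that "blood will be collected at the onset of other changes in" clinical status, with at most four such draws per patient. Appendix G, section 4.1, lists GVHD onset, the start of systemic steroids and other complications as separate sampling occasions.

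**The concern.** A diagnostic comparison needs patients who present with the same symptoms and turn out not to have GVHD. If the panel sample is taken only once systemic steroids are started, a drug rash or infectious enteritis that is recognised and not given steroids has no planned panel value at onset. The look-alikes that do have one are mainly those the clinician had already decided to treat as GVHD.

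Entry to the comparison then depends on the decision the test is meant to support. The resulting specificity describes patients started on steroids, not patients presenting with symptoms. Section 1.1 of the protocol says that GVHD often cannot be told from other causes on clinical grounds, so the presenting population is the one in which the test would be used.

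**Working it through.** **1. The passages side by side**

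| Place | Condition on the event-driven draw | Assigned to the panel? |
|---|---|---|
| 2.1 | symptoms and systemic steroids | seven-protein analysis of the appropriate samples |
| 3.4 | symptoms and systemic steroids | yes |
| Table 3 footnote | timed to systemic treatment (inpatients) | not stated |
| Appendix F, list | GVHD, symptoms needing treatment | not stated |
| Table 6, onset row | GVHD treated with systemic steroids | yes |
| 4.2, Assessments and Summary | GVHD or GVHD-like symptoms; bullet says onset of GVHD symptoms | not stated |
| 4.2, Sample Collection | acute GVHD onset; other changes in status | not stated |
| Appendix G, 4.1 | GVHD onset, steroid start, or other complications | no; cellular assays |

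Only the steroid-treated onset sample and calendar samples are assigned to the panel. Table 6 has no row for a complication draw.

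**2. What this means by type of episode**
- GVHD given systemic steroids: panel value at onset.
- Look-alike given systemic steroids and later judged not GVHD: panel value at onset under 2.1 and 3.4.
- Look-alike not given systemic steroids: blood may be drawn under 4.2, but no passage sends it to the panel.

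**3. Form of the bias**

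Let t be the share of look-alikes given steroids, and s1 and s0 the specificity in treated and untreated look-alikes. Among all look-alikes, specificity is t·s1 + (1−t)·s0. The plan as written estimates s1. The difference is (1−t)(s1−s0), and it does not shrink with sample size.

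The documents give none of these quantities. As an illustration only, take s1 = 0.60 and s0 = 0.70, the ends of Appendix C's specificity range, and assume t from 0.10 to 0.30:
- t = 0.10: 0.90 × (−0.10) = −0.09
- t = 0.30: 0.70 × (−0.10) = −0.07

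The size and even the sign depend on s1 and s0. If they are equal there is no bias.

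**4. Precision for a given number of look-alikes**

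The plan states no sample size or power for objective 2, so there is no figure to reproduce. The nearest is Appendix C's power table for the primary endpoints (N = 350, sensitivity = specificity = 0.60), which gives 0.91, 0.96 and 0.98. A two-proportion normal test, with pooled variance under the null, gives 0.913, 0.961 and 0.966 at two-sided 0.05, close to the table. At Appendix C's stated per-comparison level of 0.0012 it gives 0.523, 0.674 and 0.695. That discrepancy is a separate matter; here it means both levels should be shown.

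Appendix C's GVHD rate of 0.50 gives 350 × 0.50 = 175 cases. With m look-alikes (assumed) and sensitivity = specificity = 0.65, the test compares 0.65 with 1 − 0.65 = 0.35. The half-width is 1.96·√(0.65 × 0.35 / m).

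| m | Power, two-sided 0.05 | Power, two-sided 0.0012 | 95% half-width of specificity |
|---|---|---|---|
| 10 | 0.482 | 0.090 | 0.296 |
| 20 | 0.748 | 0.263 | 0.209 |
| 30 | 0.880 | 0.445 | 0.171 |
| 50 | 0.971 | 0.716 | 0.132 |

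For 80% power, m must be 24 at 0.05 and 60 at 0.0012.

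Where the trial falls in this table is unknown. With 415 patients accrued, assuming 15% have a look-alike episode gives 0.15 × 415 ≈ 62. If 10% to 30% of those receive steroids, m is 6 to 19. Assuming 20% with the same 30% gives 0.20 × 415 × 0.30 ≈ 25. A small change in unsupported inputs crosses the 24 needed at 0.05.

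**The case against.** A reader might infer that most look-alikes are never sampled and that objective 2 has almost no comparison group. The documents do not support that:
- Section 4.2 lists onset blood under a heading that includes GVHD-like symptoms, and its complication draws are open-ended; the examples named there are not exhaustive.
- All patients have panel-designated samples on days 7, 14, 21 and 28 (Table 6), with rash, diarrhea, nausea/vomiting and liver function staged at those visits. The acute GVHD form has differential-diagnosis boxes, and section 3.3 records biopsy results. An untreated drug rash at such a visit could have both a panel value and an alternative diagnosis.
- The frequency of look-alikes and the share given steroids appear nowhere.

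These points stand against the stronger reading, but they do not close the gap. Calendar samples, with a window of ±4 days up to day 28, are not timed to symptoms as objective 2 specifies. Those that Table 6 designates for the panel end at day 28, whereas section 1.1 puts typical GVHD onset at two to eight weeks. Complication blood has no assay assigned.

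A second tempting inference is that objective 3 loses the low end of the severity range. That is possible but not shown: the earlier validation set of 381 patients in section 1.3 were all steroid-treated and spanned onset grades 1 to 4.

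It is also fair to say that the trigger suits the primary objective, which is defined at the start of therapy. That justifies keeping this sample, not making it the only onset sample on the panel.

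**Conclusion.** The point holds as an inconsistency with a consequence. The trigger differs between 2.1, 3.4, the Table 3 footnote and Appendix F on one side and parts of 4.2 and Appendix G on the other. Untreated GVHD-like episodes are not assigned to the panel. A site and laboratory following 3.4 and Table 6 would produce a specificity estimate from a comparator group shaped by the treatment decision.

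This rests on the text alone. The numerical size does not: the number of comparators, the direction of the bias and its magnitude all need inputs that the documents lack, and the figures above are scenarios. Appendix C gives objective 2 no comparator definition, expected number or analysis. The SAP measures four markers before transplant and on days 7, 14 and 21, with no onset sample and no diagnostic comparison, so it does not repair the gap. The matter should be corrected; it concerns a secondary objective and leaves the primary objective's sampling point intact.

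**What to change.** 1. Use one trigger wording in 2.1, 3.4, Table 3, the Appendix F list and Table 6.
2. Add a Table 6 row that assigns the seven-protein panel to blood drawn at GVHD-like episodes not treated with systemic steroids, counted within the existing maximum of four complication draws.
3. Define the objective 2 comparator from the recorded biopsy result and differential diagnosis, and state its expected number.
4. Keep the therapy-initiation sample as a flagged set for the primary objective.
5. The SAP reports accrual from 2013 to 2018, so new wording cannot change collection. Run the panel on stored samples from look-alike episodes where they exist. If they do not, restrict objective 2's conclusion to patients started on systemic steroids and say so in the report.

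The cost is protocol and SAP wording, a modest number of extra ELISA runs, and some complication draws used for this purpose. The blood-volume maxima in section 4.2 do not change, because the draws fall under the four already counted (for patients over 40 kg, 4 × 15 mL = 60 mL of the 225 mL total).
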